4.0 Registration Procedures

General Guidelines for DF/HCC and DF/PCC Institutions

All participants will be registered by the DF/HCC Quality Assurance Office for Clinical Trials (QACT). Registration must occur prior to the initiation of therapy. Any participant not registered to the protocol before treatment begins will be considered ineligible and registration will be denied.

A designated member of the study team will confirm eligibility criteria and complete the protocol-specific eligibility checklist.

Once registered, any issues that would cause treatment delays should be discussed with the Principal Investigator.

If a participant does not receive protocol therapy following registration, the participant's protocol status must be changed by the study coordinator.

Registration Process for DF/HCC and DF/PCC Institutions

The QACT registration staff is accessible on Monday through Friday, from 8:00 AM to 5:00 PM Eastern Standard Time. In emergency situations when a participant must begin treatment during off-hours or holidays, call the QACT registration line at and follow the instructions for registering participants after hours.

The registration procedures are as follows:

- 1. Obtain written informed consent from the participant prior to the performance of any study related procedures or assessments.
- Complete the protocol-specific eligibility checklist using the eligibility assessment documented in the participant's medical/research record. For phase II participants, include stratification information. To be eligible for registration to the study, the participant must meet each inclusion and exclusion criteria listed on the eligibility checklist.
- 3. Fax the eligibility checklist(s) and all pages of the consent form to the QACT at
- 4. The QACT Registrar will (a) validate eligibility, (b) register the participant on the study, and (c) randomize the participant when applicable (Phase 2 part of the study). The randomization tables will be designed by the study statistician.
- 5. The QACT Registrar will send an email confirmation of the registration and/or randomization to the person initiating the registration and to the research pharmacist immediately following the registration and/or randomization.

5.0 STUDY DESIGN

- 5.1Treatment Plan
- 5.1.1 Single arm, open label, phase II study
- 5.1.2Dosing schedule

Treatment will be administered on an outpatient basis. Expected adverse events and appropriate dose modifications for sorafenib, 5-FU, oxaliplatin are as described in Section 6.0. No investigational or commercial agents of therapies other than those described below may be administered with the intent to treat the patient's malignancy.

Patients will be treated as below:

Register:

Sorafenib 400 mg bid \rightarrow	Sorafenib 400 mg bid	\rightarrow	continue treatment
First two weeks	modified folfox, days 1, 15	5	until PD or intolerable toxiity

Every 28 days/cycle

For first two weeks, sorafenib will be given alone.

Cycle 1 and beyond:

Sorafenib 400 mg bid + modified FOLFOX (Oxaliplatin 85 mg/m2 followed by leucovorin 200 mg/m², followed by infusional 5-FU at 1200 mg/m²/d on Days 1 and 2 (2400 mg/m² total over 46 hours) repeated every 14 days for each cycle.

Oxaliplatin will be delivered at 85 mg/m²as a 2-hour infusion on day 1 and day 15 of every cycle.

Drugs 5-FU/LV		Oxaliplatin	Sorafenib
Treatment dates	Days 1,15	Days 1,15	Daily (days 1-28)
Dosage	LV: 200 mg/m2 5-FUCI: 2400 mg/m ² total (1200mg/m ² /d on day 1 and 2)	85 mg/m2	400 mg bid

Lead-in sorafenib alone treatment: first 2 weeks.

Each cycle is defined as 28-day treatments.

5.1.3 Estimated number of patients

40 patients with advanced HCC

- 5.1.4Estimated rate of accrual
 - 2-3 patients each month
- 5.1.5. Estimated date of study completion

Estimated date of study completion is July 2013 with an estimated start date of July 2012

5.1.6Duration of therapy

In the absence of treatment delays due to adverse events, treatment may continue until one of the following criteria applies:

- Disease progression
- Intercurrent illness that prevents further administration of treatment
- Unacceptable adverse event(s)
- Patient decides to withdraw from study
- General or specific changes in the patient's condition render the patient unacceptable for further treatment in the judgment of the investigator

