14.0 STATISTICAL CONSIDERATIONS

14.1 Target Sample Size

Forty patients will be entered in this phase II study. Assuming the accrual rate is 2-3 patients per month, the accrual will be completed in 18 months or less.

- 14.2Planned Efficacy Evaluations
 - 14.2.1 Primary Efficacy Variables

The primary objective of this study is time to tumor progression (TTP). A sample size of 40 achieves 80% power to detect the difference between the null hypothesis median TTP of 5 months and an alternative hypothesis median TTP of 7 months at a 10% significance level using a one-sided test based on the elapsed time, assuming a study follow-up period of 24 months. The total study duration will be 42 months (18 months of accrual + 24 months of follow-up).

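### Do the July 2013 completion date and the 18-month accrual figure undermine the 80% power for time to progression?

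*Combined protocol and SAP*

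**What the plan says.** Three places in the combined protocol and SAP bear on the timeline.

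- **Section 5.1.5:** "Estimated date of study completion is July 2013 with an estimated start date of July 2012". Sections 5.1.3 and 5.1.4, just above it, give "40 patients with advanced HCC" and an accrual of two to three a month.
- **Section 14.1:** "Forty patients will be entered in this phase II study", and "Assuming the accrual rate is 2-3 patients per month, the accrual will be completed in 18 months or less".
- **Section 14.2.1:** "A sample size of 40 achieves 80% power to detect the difference between the null hypothesis median TTP of 5 months". The alternative is a 7-month median, with a one-sided 10% test and an assumed 24 months of follow-up. It then says "The total study duration will be 42 months (18 months of accrual + 24 months of follow-up".

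Section 5.1.1 describes the design as "Single arm, open label, phase II study", so the power rests on a comparison with a fixed historical median. The title page dates this version 24 February 2015.

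**The concern.** The power for a time-to-event endpoint comes from events, so the calendar is a design input. Counted from July 2012, 42 months ends in January 2016, which is 30 months after the date in Section 5.1.5. That date does not work as the end of accrual either: 12 months at two to three a month brings in 24 to 36 patients, not 40.

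Section 14.1 has a smaller slip of the same kind. Its 18-month limit fails at the lower end of its own accrual range.

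Section 14 names no event count or data cut-off date for the primary analysis. A reader could therefore fear that the study would be closed on the Section 5.1.5 date with too few patients and far too few progressions, leaving about an even chance of detecting the effect the trial was sized for.

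**Working it through.** **Inputs.** From Sections 14.1 and 14.2.1: N = 40; median time to progression 5 months (null) and 7 months (alternative); one-sided alpha 0.10; accrual A = 18 months; further follow-up F = 24 months; 2 to 3 patients a month. From Section 5.1.5: July 2012 to July 2013, 12 months. Assumptions added here: exponential times, uniform accrual, no dropout, and progression observed when it occurs.

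**1. Accrual time.** 40/2 = 20 months; 40/2.5 = 16 months; 40/3 = 13.3 months. Finishing in 18 months needs 40/18 = 2.22 a month. At 2 a month, 18 months gives 36 patients.

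**2. Reproducing the stated 80%.** With λ = ln 2/7 = 0.0990 a month, the chance that a patient has an event by the analysis is

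p = 1 − [exp(−λF) − exp(−λ(A+F))]/(λA).

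For A = 18 and F = 24: p = 1 − (0.0929 − 0.0156)/1.782 = 0.957, so d = 40 × 0.957 = 38.3 events.

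The exact exponential test has power P(χ² > q × 5/7), where χ² has 2d degrees of freedom and q is its 0.90 quantile. The result is 79.3%. Other calculations agree:

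- If all 40 patients have events: 80.5%.
- Normal approximation on the log hazard: Φ(√38.3 × ln(7/5) − 1.2816) = Φ(0.80) = 78.8%.
- Simulation of 100,000 trials with the test calibrated to 10%: 79.8%.

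The hazard-scale approximation is the lowest of the variants tried, at 76.0%. The plan's 80% is reproduced on its own inputs.

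**3. Effect of the accrual slip**, by the same formulas:

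| Scenario | Events | Power |
|---|---|---|
| Plan: 40 patients, 18 + 24 months | 38.3 | 79.3% |
| 40 patients, 20 + 22 months (total held at 42) | 38.0 | 79.1% |
| 40 patients, 20 + 24 months (total 44) | 38.4 | 79.4% |
| 40 patients, 13.3 + 24 months (total 37.3) | 37.9 | 79.1% |
| Accrual closed at 36, 18 + 24 months | 34.4 | 76.3% |

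With 40 patients, power stays within 0.3 points over the whole stated accrual range. The 36-patient row would mean departing from the stated target.

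**4. The feared case: data cut-off at month 12.** With A = 12 and F = 0, p = 1 − (1 − 0.305)/1.188 = 0.415.

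| Rate per month | Patients | Events | Power |
|---|---|---|---|
| 2 | 24 | 10.0 | 43.9% |
| 2.5 | 30 | 12.4 | 48.6% |
| 3 | 36 | 14.9 | 52.9% |

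That is 26% to 39% of the 38.3 planned events. Across standard test variants the range is about 36% to 53% for 24 patients and 47% to 61% for 36.

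**5. Does anything in the document lead to step 4?** Section 5.1.5 offers an estimate, does not define completion, and mentions no analysis. Section 14.2.1 states the follow-up and total duration on which the test is planned. The version date of February 2015 is 19 months after July 2013, so a reader of this version could not close the study on that date. The date is also incompatible with the patient number and accrual rate given immediately above it, which marks it as an entry carried forward without updating.

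**The case for a change.** The strongest case for a change is that Section 14 sets no event trigger or cut-off date, so the duration statements are the only guide to when the primary analysis happens, and they differ by 30 months. Correcting them would alter a few figures and affect no patient. The power loss at month 12 would be severe, and the inconsistency survived into a version issued after the estimated date had passed.

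Much of this stands. The two timelines disagree, nothing reconciles them, and the 18-month limit is false below 2.22 patients a month.

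What does not stand is the consequence. The two statements do not carry equal weight on analysis timing: one is an administrative estimate, and the other is the stated basis of the power calculation. The 44% to 53% needs a cut-off that the document nowhere prescribes and that had already lapsed. The figures are also less firm than they look, because they depend on the choice of test and on progression being seen at once. Section 5.2.2 puts the first scan at the end of cycle 2, about 10 weeks after treatment starts, which matters when follow-up runs from 0 to 12 months. Adding a formal rule for analysis timing would be a separate request, not the correction of a date.

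**Conclusion.** No change to the plan follows. The Section 5.1.5 date is a clerical leftover, and the 18-month accrual figure is slightly optimistic at the slow end of its range.

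The power statement is sound on its own inputs, at about 79% against the stated 80%. It moves by at most 0.3 points if all 40 patients are enrolled over anything from 13.3 to 20 months. Even the unfavourable reading, accrual stopped at 36, costs about 3 points. The large loss belongs only to a hypothetical cut-off at month 12.

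This rests on the assumptions listed with the calculation, and on reading Section 14 as governing the analysis: 40 patients and 24 months of follow-up after accrual. An analyst working from Section 14 would use the same patients and follow-up, and reach the same conclusion, with or without a corrected date.

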5.2 CLINICAL AND LABORATORY EVALUATIONS

5.2.1 Pre-Treatment Evaluations

Signed and informed consent should be obtained prior to specific protocol testing and evaluation. The following evaluations must be performed prior to each patient's first dose of sorafenib:

5.2.1.1 Evaluations that must be performed within 1 week prior to the first dose of sorafenib:

• Pregnancy test (serum or urine) for women of childbearing potential within 7 days prior to initiation of therapy.

5.2.1.2 Evaluations that must be performed within 2 weeks prior to the first dose of sorafenib:

- Medical history
- Physical examination, including vital signs, height, weight, performance status.
- Hematology: complete blood count (CBC) with differential.

• Serum Chemistries: glucose, BUN, creatinine, uric acid, total bilirubin, alkaline phosphatase, LDH, total protein, albumin, SGOT(AST), SGPT (ALT), calcium, phosphorus, amylase, lipase, and AFP.

• PT/INR

• Hepatitis B surface antigen, core antibody, and surface antibody, and Hepatitis C antibody must be obtained within 120 days of study enrollment.

Urinalysis: urine dipstick for protein. Patients with a positive dipstick for urine protein (reading of 2+ or greater) will then undergo a 24 hour urine collection for protein.

*If the screening labs have been completed within 7 days of Day 1 of the lead-in period, these labs do not need to be repeated. However, baseline correlative studies need to be drawn on Day 1 of the lead-in period.

5.2.1.3 Evaluations that must be performed within 3 weeks prior to the first dose of sorafenib:

• EKG

S-FOLFOX in HCC

• Imaging: Baseline radiologic evaluation of tumor burden by chest/abdomen/pelvis CT scan. MRI of the liver can be used if patients have an IV contrast allergy or the CT scan is suboptimal based on the physician's judgment.

5.2.2 Evaluations During Treatment

- Monitor CBC and selected chemistries (Glucose, BUN, Creatinine, ALT, AST, ALKP, total bilirubin, calcium, phosphorus, LDH, protein, albumin) weekly during the first 5 weeks of therapy (during the initial two weeks of sorafenib treatment and the first 3 weeks of Cycle 1 of FOLFOX-sorafenib) and every two weeks after that. Urinalysis and AFP will be performed prior to each cycle.
- Imaging: Radiologic evaluation (CT or MRI scan) by RECIST 1.1 criteria will be performed at the end of cycle 2 of FOLFOX-sorafenib and every 2 cycles thereafter.

All non-radiological assessments must be performed prior to administration of any study medication. All study assessments should be done within +/- 3 days of the protocol-specified date, unless otherwise noted.

All radiological assessments should be done within +/7 days of the protocol specified date, unless otherwise noted.

5.2.3 Post-Treatment Evaluations

- All patients will be evaluated by history and physical examination, including vital signs, weight, and performance status, CBC with differential, chemistries, and reassessment of tumor at the end of treatment.
- Female patients of childbearing potential will be evaluated with a repeat pregnancy test at end of treatment visit.
- All sites of tumor progression and metastasis will be recorded.
- Progression-free and overall survival will be determined.
- 5.2.4 Correlative Studies
 - Only patients getting their treatment at MGH will be eligible for the correlative studies given that all samples need to be processed at the Steele Lab at MGH.
 - BASELINE AND ON-TREATMENT PLASMA STUDIES (see Appendix C for details): Circulating endothelial cells and plasma levels of growth factors will be assessed:
 - On Day 1 (prior to the first dose of sorafenib) and Day 3 of lead-in phase
 - On C1D1, C1D15, and C1D29 of FOLFOX-Sorafenib. The Day 3 correlative can be drawn on Day 3, 4, or 5. The Day 15 correlative can be drawn on Day 14, 15, or 16. The Day 29 correlative can be drawn on Day 27, 28, or 29.
 - At the time of progression if available

 ON-TREATMENT OPTIONAL BIOPSY (see Appendix D for details): All patients enrolled on this trial are required to have a baseline diagnostic biopsy for histological confirmation of HCC. To be considered for the optional posttreatment tumor biopsy, the patient must have adequate tissue on their baseline biopsy (i.e. core biopsy) to have all necessary correlative studies run on the sample. The optional posttreatment tumor biopsy will be obtained any time from Day 10 to Day 14 of the lead-in phase in patients who consent to a posttreatment tumor biopsy (n=6-12).

6.0 DOSE MODIFICATION / TOXICITY MANAGEMENT

Study drug treatment will be modified in the event of certain adverse events, as shown in the tables below.

- Regardless of the reason for holding study drug treatment, the maximum allowable length of treatment interruption of FOLFOX is 6 weeks (the holding of 3 consecutive doses) and of Sorafenib is 3 weeks. If the patient needs to stop FOLFOX due to toxicity, they can stay on study as long as they continue with Sorafenib. If the patient needs to stop Sorafenib due to toxicity, they can stay on the study as long as they continue FOLFOX. If they need to stop both FOLFOX and Sorafenib for longer than the above time limits, they must be taken off the study and the Principle Investigator must be notified.
- Doses of chemotherapy that have been reduced will not be re-escalated.
- No held doses of Sorafenib or FOLFOX will be made up. If a patient misses a dose for toxicity, the patient will proceed to the next treatment day or cycle as scheduled.

6.1 Expected Adverse Events – 5-FU

Nausea, vomiting (mild); ileus, stomatitis (5-8 days after treatment initiation); gastric ulceration; myelosuppression: leukopenia, granulocytopenia (9-14 days); thrombocytopenia (7-14days); alopecia; loss of nails; hyperpigmentation; photosensitivity; maculopapular rash; palmar-plantar erythrodysethesias (42-82% receiving continuous infusion); CNS effects: disorientation, confusion (rare); cardiotoxicity: MI, angina, asymptomatic S-T changes (68%); rare ocular effects.

6.2 Oxaliplatin

In the second line therapy for metastatic colorectal cancer registration trial of oxaliplatin, the following adverse reactions were reported to occur in greater than or equal to 5% of all patients.

	Oxaliplatin		Oxaliplatin + 5-FU/LV	
Adverse	All Grades	Grade 3 or	All Grades	Grade 3 or
Event	(%)	4 (%)	(%)	4 (%)
Fatigue	52 %	9 %	68 %	7 %
Diarrhea	46	4	67	11
Nausea	64	4	65	11
Neuropathy	76	7	73	7
Acute	65	5	56	2
Persistent	43	3	48	6
Vomiting	37	4	40	9
Stomatitis	14	0	37	3
Abdominal	31	7	33	4
pain				
Fever	25	1	29	1
Anorexia	20	2	29	3
Dyspnea	13	7	20	4
Back pain	11	0	19	3
Coughing	11	0	19	1
Edema	10	1	15	1
Pain	14	3	15	2
Injection	9	0	10	3
site reaction				
Thrombo-	2	1	9	8
embolism				
Hypokalemi	3	2	9	4
а				
Dehydration	5	3	8	3
Chest pain	5	1	8	1
Febrile	0	0	6	6
neutropenia				
GERD	1	0	5	2
	Oxa	liplatin	Oxaliplat	in + 5-FU/LV
Adverse	All Grades	Grade 3 or	All Grades	Grade 3 or
Event	(%)	4 (%)	(%)	4 (%)
Constipatio	31	<1	32	<1
n				
Headache	13	<1	17	<1
Rhinitis	6	<1	15	<1
Dyspepsia	7	<1	14	<1
Taste	5	<1	13	<1
Perversion				

Dizziness	7	<1	13	<1
Hand-foot	1	<1	11	<1
syndrome				
Flushing	3	<1	10	<1
Peripheral	5	<1	10	<1
edema				
Allergic	3	<1	10	<1
reaction				
Arthralgia	7	<1	10	<1
Upper resp.	7	<1	10	<1
tract infect.				
Pharyngitis	2	<1	9	<1
Rash	5	<1	9	<1
Insomnia	11	<1	9	<1
Epistaxis	2	<1	9	<1
Mucositis	2	<1	7	<1
Alopecia	3	<1	7	<1
Abnormal	1	<1	7	<1
lacrimation				
Rigors	9	<1	7	<1
Hematuria	0	<1	6	<1
Dysuria	1	<1	6	<1
Hiccup	2	<1	5	<1
Flatulence	3	<1	5	<1

6.3 Dose Modification of 5-FU and Oxaliplatin

6.3.1 Toxicity will be evaluated weekly during the sorafenib lead-in period, weekly during the first 3 weeks of cycle 1 of FOLFOX-Sorafenib, and then once every two weeks for subsequent cycles. Dose modifications based on significant weight changes can be made in accordance to institutional practice.

6.3.2 Hematologic Toxicity

- CBC will be obtained on days 1 and 15 of each cycle.
- Patient must have ANC > 1000 and platelets > 75,000 in order to treat on any given treatment day.

C1D1 dosing AND subsequent Day 1 and Day 15 dosing if previous dose was given:

ANC Platelets		%Previous dose 5-	%Previous dose		
		FU/LV	Oxaliplatin		
>1000 and	>75,000	100	100		

≤1000	≤75,000	HOLD dose and	HOLD dose and
		reassess in 2 weeks	reassess in 2 weeks
≤500	≤50,000	HOLD dose and	HOLD dose and
		reassess in 2 weeks	reassess in 2 weeks

Day 1 and 15 dosing if the immediate previous Day 1 or 15 dose was HELD:

ANC	Platelets	%Previous dose 5- FU/LV	%Previous dose Oxali
>1000 and	>75,000	75% of previous dose if either ANC was 501-1000 or Plts were 51,000- 75,000 50% of previous dose if either ANC was ≤500 or Plts	75% of previous dose if either ANC was 501-1000 or Plts were 51,000- 75,000 50% of previous dose if either ANC was ≤500 or Plts
<1000 or	<75.000		
≥1000 or	≥75,000	reassess in 2 weeks	reassess in 2 weeks
≤500 or	≤50,000	HOLD dose and reassess in 2 weeks	HOLD dose and reassess in 2 weeks

If the patient requires two consecutive doses of FOLFOX to be held for hematologic toxicity, the patient should get 50% of the previous dose of FOLFOX if they meet criteria for treatment on the next scheduled treatment day.

In addition, at any time during a cycle, if the patient experienced 1) febrile neutropenia or 2) any Grade 3 or higher hematologic toxicity (excluding thrombocytopenia and neutropenia, which will be addressed using the tables above) while on FOLFOX, then 5-FU and Oxaliplatin should be held until the toxicity resolves to <Grade 2. When the patient meets treatment criteria, the 5-FU and Oxaliplatin should be resumed at 75% of most recent dose for all subsequent doses.

Doses of chemotherapy that have been reduced will not be re-escalated. A maximum of 4 dose reductions are allowed for 5-FU and Oxaliplatin (with the minimum allowed dose of 5-FU being 380 mg/m2/day and the minimum allowed dose for oxaliplatin being 27 mg/m2).

No held doses will be made up. If a patient misses a dose for toxicity, the patient will proceed to the next treatment day or cycle as scheduled.

If the FOLFOX is held for > 6 weeks (i.e. three consecutive doses of FOLFOX are held), FOLFOX will be permanently discontinued, and the patient can remain on the study as long as they are receiving Sorafenib.

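### Section 6.3.2 gives two unreconciled FOLFOX restart doses, 50% and 75%, for a patient who loses two consecutive doses to a hematologic toxicity other than neutropenia or thrombocytopenia

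*Combined protocol and SAP*

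**What the plan says.** Section 6.3.2 sets FOLFOX restart doses in three places.

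- **Held-dose table.** For a patient whose previous dose was held and whose counts have recovered, one line gives "75% of previous dose if either ANC was 501-1000 or Plts were 51,000- 75,000". The next gives "50% of previous dose if either ANC was ≤500 or Plts", where the text available to us breaks off.
- **Two-dose sentence, directly below the table.** "If the patient requires two consecutive doses of FOLFOX to be held for hematologic toxicity, the patient should get 50% of the previous dose", provided the treatment criteria are met on the next scheduled day. The sentence does not limit the kind of hematologic toxicity.
- **Paragraph opening with 'In addition'.** Its triggers include "any Grade 3 or higher hematologic toxicity (excluding thrombocytopenia and neutropenia, which will be addressed using the tables above) while on FOLFOX". Both drugs are held until the toxicity is below Grade 2, and then "the 5-FU and Oxaliplatin should be resumed at 75% of most recent dose for all subsequent doses". The number of doses held plays no part.

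The same section adds: "Doses of chemotherapy that have been reduced will not be re-escalated". Section 6.3.3.5 only refers hematologic toxicity back to 6.3.2, so no order of precedence is given there either.

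**The concern.** The two-dose sentence and the 'In addition' paragraph overlap. A patient with Grade 3 anemia that has not recovered by the second scheduled dose has lost two consecutive doses to a hematologic toxicity, which points to 50%. The same patient has had a Grade 3 hematologic toxicity that is neither neutropenia nor thrombocytopenia, which points to 75%. Two investigators who both follow the protocol could give different doses to patients with the same blood counts.

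Because reductions are permanent, the choice carries through the rest of that patient's FOLFOX. Under one of the readings the patient receives a dose that the authors did not intend. Tolerability is a secondary objective (section 1.2), and adverse events are harder to interpret if the dose behind them depends on how a sentence was read.

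The held-dose table may hold a similar overlap: as far as it can be read, both of its lines are satisfied by *either* count.

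**Working it through.** **1. Inputs.** Oxaliplatin: "Oxaliplatin will be delivered at 85 mg/m²as a 2-hour infusion on day 1 and day 15 of every cycle" (section 5.1.2). 5-FU: 1200 mg/m²/day on two days, 2400 mg/m² in total (section 5.1.2). Stated minimum doses: 5-FU 380 mg/m²/day and oxaliplatin 27 mg/m², with at most four reductions (section 6.3.2). Hemoglobin grades: Grade 2 from 8.0 to below 10.0 g/dL, Grade 3 from 6.5 to below 8.0 g/dL (section 6.4.1).

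**2. The plan's own figures.** The stated minimums are four successive 25% reductions:
- 5-FU: 1200 × 0.75⁴ = 379.7, stated as 380.
- Oxaliplatin: 85 × 0.75⁴ = 26.9, stated as 27.

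These reproduce.

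**3. Can a patient meet both rules?** Recovery to below Grade 2 means hemoglobin of at least 10.0 g/dL on the section 6.4.1 grades, which is also the entry minimum in section 3.1. Doses fall two weeks apart. A patient below 8.0 at one scheduled dose and still below 10.0 at the next has missed two. Restart after that is allowed, since section 6.0 says "the maximum allowable length of treatment interruption of FOLFOX is 6 weeks (the holding of 3 consecutive doses"), and 6.3.2 ends FOLFOX only when three consecutive doses have been held. The overlap is therefore a permitted path through the protocol.

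**4. Size of the difference, from full dose.**
- Oxaliplatin: 85 × 0.50 = 42.5 mg/m²; 85 × 0.75 = 63.75 mg/m².
- 5-FU per administration: 2400 × 0.50 = 1200 mg/m²; 2400 × 0.75 = 1800 mg/m².
- Ratio: 0.50 / 0.75 = 0.667, so the lower reading gives one third less than the higher.

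**5. Room left above the stated minimums.** After a 75% restart (5-FU 900 mg/m²/day, oxaliplatin 63.75 mg/m²), three further 25% steps reach 379.7 and 26.9, the minimums themselves. After a 50% restart (600 and 42.5), one further 25% step gives 450 and 31.9; a second gives 337.5 and 23.9, below both minimums.

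**6. The held-dose table as visible.** Take three bands for each count: ANC above 1000, 501–1000, and 500 or less; platelets above 75,000, 51,000–75,000, and 50,000 or less. Of the nine pairs, eight have at least one low count. Two of the eight satisfy both lines:
- ANC 500 or less with platelets 51,000–75,000, for example ANC 400 and platelets 60,000. This uses only visible text.
- ANC 501–1000 with platelets 50,000 or less. This assumes that the lost platelet limit is the 50,000 shown in the hold row.

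The other six give a single answer.

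**7. Link to the sample size.** Section 14.2.1 uses medians of 5 and 7 months, one-sided 10% significance and 80% power. Under an exponential one-sample approximation, (1.2816 + 0.8416)² / [ln(7/5)]² = 39.8 events, in line with the planned 40 patients. No restart dose enters this calculation.

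**The case against.** The best counter-reading of the main conflict is contextual. The two-dose sentence stands under the neutrophil and platelet tables and depends on meeting treatment criteria, which 6.3.2 sets out as ANC and platelet limits. The next paragraph opens as an addition and carries its own hold and restart rule. On that reading the sentence completes the tables, the paragraph governs everything else, and anemia never reaches the two-dose rule. This is plausible, but it is not written. The sentence speaks of hematologic toxicity without limit, although the following paragraph names its exclusions when it wants them. One could equally read the sentence as a stricter rule that overrides 75%. These two readings lead to different doses.

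Section 4.0 asks that issues causing treatment delays be discussed with the principal investigator. That should bring many such cases to one decision-maker and lowers the risk of uneven practice, but it states no dose.

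On the table, much of the objection stands. The 50% line is cut off, and a qualifier may have been lost with the platelet figure. Many clinicians would also let the worse count govern. Text lost in extraction cannot be held against the plan, so this part stays secondary.

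A reader might infer that the problem will be common, from the neutropenia rate reported for the sorafenib, capecitabine and oxaliplatin trial in section 2.4. The documents do not support that. The rate is ungraded and comes from another regimen. The main conflict excludes neutropenia by its terms, and the table overlap needs two counts low at different depths.

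**Conclusion.** The text is wrong as written: it contains an internal contradiction in a dosing rule. For a hematologic toxicity of Grade 3 or higher, other than neutropenia or thrombocytopenia, that costs two consecutive FOLFOX doses, 6.3.2 prescribes both 50% and 75%. The gap is one third of the higher dose, and it is permanent. This rests on reading the two passages literally and, for the anemia example, on applying the hemoglobin grades of section 6.4.1 to FOLFOX.

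The table overlap is conditional. It holds on the visible wording and stands only if the original cell reads the same way.

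The frequency is unknown. The documents give no rate for Grade 3 anemia or for mixed cytopenias on this regimen, and few of the 40 patients may be affected. A reader might go further and infer that the contradiction undermines the time-to-progression result. Nothing in the documents shows that: the sample size does not depend on it, and no effect on progression can be derived. The concern is patient safety and uniform dosing for the tolerability objective. It should be corrected, mainly because correction is nearly free.

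**What to change.** Reconcile the passages in 6.3.2. State which rule governs when two consecutive FOLFOX doses are held for a hematologic toxicity other than neutropenia or thrombocytopenia. Check the held-dose cell in the original protocol; if it reads as it does here, reword its two lines so that every pair of ANC and platelet values falls under exactly one. Which percentage applies in each case is for the investigator to decide, and this review takes no position on it.

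The cost is a few words in one section by amendment, with no new data, visits or patients.
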